9.1 Number of patients to enroll

Up to 150 patients fulfilling the inclusion and exclusion criteria will be enrolled in the study. At least 56 subjects passing screening will be randomized. All sites are allowed to recruit patients competitively according to their possibilities. Patient screening and enrollment will be performed in close collaboration with the sponsor to avoid over-recruitment.

Potential patients will be called by the participating centers and may be pre-screened for study eligibility. In addition, patients contacting the centers or visiting them on a routine basis can be also pre-screened.

Once a potential participant using a unilateral KAFO or SCO has been identified, study clinician may contact the potential patient or study staff will contact the potential patient on behalf of the principal investigator, starting with a letter followed by a phone call to the potential patient.

A screening log will be tracked.

9.2 Duration individual patient's participation

Each patient should be observed 8-9 months depending on which orthosis is used before the crossover.

9.3 Inclusion and Exclusion Criteria:

Patients must meet all of the inclusion and must not meet any of the exclusion criteria to be registered to the study.

Study treatment may not begin until a patient is registered.

9.3.1 Inclusion criteria

- Patient has been tested with the Trial Tool (DTO) and demonstrated the potential to utilize the C-Brace successfully (see section benchmarks: independent donning/doffing of the orthosis, charging of the device, transfers sit to stand/stand to sit, standing in the orthosis with or without assisted device for a minimum of 2 minutes, safe over ground ambulation, ambulatory turns and to perform a swing phase).
- Patient has a BBS score < 45
- Lower limb functional impairment according to CE label wording
- Prior active and compliant use of unilateral or bilateral KAFO or SCO in the past 3 months prior to enrollment in the study
- Patient meets minimum physical requirements to be fitted with a C-Brace, such as muscle status, joint mobility, leg axis and proper control of the orthosis must be guaranteed.

ottobock.	CLINICAL INVESTIGATION PLAN	Document number:	PD-PS00120016A-001
		Version number:	7
Project name	Clinical trial comparing C-Brace to KAFO/SCO	Project no.	PS00120016A

- The User must fulfill the physical and mental requirements for perceiving optical/acoustic signals and/or mechanical vibrations
- The existing muscle strength of the hip extensors and flexors must permit the controlled swing-through of the limb (compensation using the hip is possible).
- Patient's commitment to use C-Brace 2 at least 1-2 hours per day 5 days per week-
- Patient is ≥ 18 years old
- Patient is willing and able to independently provide informed consent.
- Person is willing to comply with study procedures

9.3.2 Exclusion criteria

- Patient who is not able to follow the entire study visits or is unwilling/unable to follow the instructions
- Patient was not able to use DTO
- Patient who is not using an orthosis at least 1 to 2 hours/ day for 5 days per week
- Patient with body weight > 125 kg (includes body weight and heaviest object (weight) carried)
- Patient with Orthoprosthesis
- Patient with flexion contracture in the knee and/or hip joint in excess of 10°
- Patient with uncontrolled moderate to severe spasticity (relative contraindication moderate spasticity)
- Leg length discrepancy in excess of 15 cm
- Patient with unstable neurological or cardiovascular/pulmonary disease, cancer
- Pregnancy
- Patient using a C-Brace
- Patient with known vertigo or with history of falls unrelated to orthosis use or unrelated to motor disability
- Patient who has never been fitted an orthosis before
- Patient is not able to answer the self-administered questionnaires independently; for patients with upper extremity impairment is it allowed to verbally answer the questions.
- Patient participating already in a clinical study during this study's duration
- Patient participated in earlier C-Brace studies

Additional determination of exclusion criteria for Austrian centers:

Pregnant and nursing women are NOT allowed to participate in this study.

Women of childbearing age are only allowed to participate in this study, if they have confirmed that they are not pregnant before the study (according to a pregnancy test). They will be asked to perform pregnancy tests once a month during the study. Female patients will be asked to inform the investi-

ottobock.	CLINICAL INVESTIGATION PLAN	Document number:	PD-PS00120016A-001
		Version number:	7
Project name	Clinical trial comparing C-Brace to KAFO/SCO	Project no.	PS00120016A

gator immediately, if they become pregnant during the study, or suspect that they are pregnant. Their participation in the study will be terminated under these circumstances.

9.3.3 Drop out or early termination of the study

Patients can withdraw from the study at any time and for any reason. This decision has no impact on the patient's medical care. In case of early termination, the investigator must document the reasons as completely as possible. The investigator can temporarily or permanently discontinue the patient's study participation for any reasons that are in the patient's best interest, particularly in cases of serious adverse events. If a patient is lost to follow-up, the investigator will use all available means to get into contact with him or her. After three weekly telephone reminders, the patient will be recorded as lost to follow-up.

The investigator will fill in the reason for the drop out or early termination of follow-up in the case report form. Patient who drop out of the study may not keep the C-Brace up to 24 months as described in section 7.3.10.

Dropouts will be replaced until the milestone last patient in was reached.

10 Statistics

The goal of this study is to assess the improvement of static and dynamic balance by using C-Brace compared to KAFO/SCO which should in consequence help reduce the risk of falling/falls in these patients.

10.1 Sample size calculation

The sample size calculation is based on the hypothesis as described in 6.2 and crossover study design as described in 7. The number of recruited patients however will be larger than what would be needed to fulfill the requirements of the primary efficacy endpoint in order to achieve a higher power for any tests performed on secondary objectives and to improve the likelihood that the random allocation of patients results in similar baseline characteristics in the compared group.

Sample size calculation was performed with G*Power 3.1.9.7 or manually as described.

ottobock.	CLINICAL INVESTIGATION PLAN	Document number:	PD-PS00120016A-001
		Version number:	7
Project name	Clinical trial comparing C-Brace to KAFO/SCO	Project no.	PS00120016A

10.1.1 Primary efficacy endpoint

The efficacy of the microprocessor based C-Brace technology compared to a non-microprocessor controlled KAFO/SCO will be determined through the detection of a statistically significant improvement of the Berg Balance Scale.

One null-hypothesis will be tested in the confirmatory analysis:

$$H_0: \Delta \text{Berg Balance Scale} \leq 0$$

$$H_1: \Delta \text{Berg Balance Scale} > 0$$

Sample size calculations are based on a mean group difference $\Delta = 6.6429$ between the C-Brace technology compared to a non-microprocessor controlled KAFO/SCO and a standard deviation $\sigma = 4.9085$ of this difference.

The estimations of the parameters come from paired observations in the RIC study combined with the paired observations of 4 patients from the Wien/Goettingen study (RIC combination study). In total, 14 patients in the RIC combination study were considered to determine the estimates. All the included patients displayed a Berg Balance Scale of less than 45.

To test the hypothesis of an expected effect in one direction a one-tailed paired t-test will be used.

At an α level of 0.05 and a power of 0.8, a total of 6.4557 of patients are needed as calculated from the t-distribution. Under the assumption of a dropout rate of 20% a total of 9 patients would need to be recruited.

10.1.2 Secondary endpoints

An improvement in patients balance is hypothesized to aid the patients in their daily life and potentially influence some of the other outcome measures collected in this study. These measures will be explored without a strict expectation for the magnitude of expected change. Due to the expected nature of the distribution of the number of falls or rather the proportion of patients to fall more than once with the device C-Brace, these measurements would require the largest sample size in order to detect significant improvements at a reasonable power level.

If the probability to fall more than once with the device C-Brace is significantly lower than the probability to fall more than once with the device KAFO/SCO it could be used as a supporting argument to relevance of a potentially identified improvement in the primary efficacy endpoint. Previous observations on the RIC combination data however revealed a low expectancy of the probabilities to fall more than once with either KAFO/SCO and C-Brace device during the observed time span. A probability to fall more than once of $P_{KAFO/SCO} = 0.1333$ with the device C-Brace and a probability to fall more

ottobock.	CLINICAL INVESTIGATION PLAN	Document number:	PD-PS00120016A-001
		Version number:	7
Project name	Clinical trial comparing C-Brace to KAFO/SCO	Project no.	PS00120016A

than once of $p_{C-Brace} = 0$ for the device KAFO/SCO was recorded for 15 paired observations in the RIC combination study.

The sample size needed to detect a difference of $p_{diff} = p_{KAFO/SCO} - p_{C-Brace} = 0.1333$ for the paired proportions with on the basis of one-sided McNemar's Z-test without continuity correction is calculated as

$$n = \left(\frac{z_{1-\alpha} \sqrt{p_{disc}} + z_{1-\beta} \sqrt{p_{disc} - p_{diff}^2}}{p_{diff}} \right)^2$$

where $p_{disc} = p_{KAFO/SCO} + p_{C-Brace} = 0.1333$

At a significance level of 0.05 and a power of 0.8, a total of 44.2386 of patients would be needed. Under the assumption of a dropout rate of 20% a total of 56 patients would need to be recruited. We recognize that the inclusion of a continuity correction may be more appropriate given the small proportion to fall more than once with either type of device and that a shift in the expected proportions away from zero would drastically increase the number of patients needed to detect the difference to show a significant difference. Regardless the merit of the observing these proportions at a higher absolute occurrence will yield a sound basis for future studies. For this reason, the number of patients to be included in the study is based on this value.

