10.3.1 Secondary outcome analysis

Analyses for the secondary outcome measures will be performed for the intention-to-treat population as well as for the per-protocol population. All inferential analyses for the secondary efficacy variables will be interpreted in the exploratory sense. All secondary outcome measures will be evaluated by using descriptive statistics primarily, absolute values at each time point and if appropriate changes from first baseline and follow ups respectively. These analyses will be performed in a similar way as the primary efficacy outcome using a linear mixed effects model when appropriate.

Additional attention will be paid to the exploration of the measurements of safety and falls. The number of Falls is expected to be reduced in general by using a C-Brace, but the extent of a possible reduction remains uncertain. Therefore, frequency of falls, severity of falls, fall-related injuries, fear of falling and related treatment efforts will be explored in rigorously in order to formulate appropriate hypothesis for future research.

In the past the reduced probability of falling more than once by using C-Brace compared to KAFO / SCO showed the most promise as a reliable measure to compare the two device types, since it was less sensitive to outliers e.g. patients with a high number of falls on either device as compared to the total number of falls. However, sample sizes in prior research were relatively small and estimations for potential differences remain uncertain, albeit of great clinical interest.

Therefore, we explore whether a reduction in the probability of falling more than once using the C-Brace can be detected by a McNemar Test for paired proportions. This test will likely be underpowered in comparison to the expected best-case scenario used in the sample size calculation and will be reported accordingly.

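### The power of 0.8 that sets the trial size at 56 is not the real power of the planned McNemar test, and the analysis section does not say which version will be run

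*Combined protocol and SAP*

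**What the plan says.** By the plan's calculation in section 10.1.1, the primary endpoint needs only 9 recruited patients. The trial size therefore comes from section 10.1.2, on the probability of falling more than once.

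- **Planning rates:** 0.1333 on KAFO/SCO and 0 on C-Brace. The pair "was recorded for 15 paired observations in the RIC combination study".
- **Test used for sizing:** "one-sided McNemar's Z-test without continuity correction", with both the difference and the discordant proportion set to 0.1333.
- **Result:** "At a significance level of 0.05 and a power of 0.8, a total of 44.2386 of patients would be needed". A 20% dropout allowance takes this to 56, and the section says the number of patients rests on this value.
- **Caveat:** "We recognize that the inclusion of a continuity correction may be more appropriate". The section adds that rates away from zero would raise the requirement sharply. It gives no figure for either point.
- **Analysis:** section 10.3.1 (Secondary outcome analysis) will explore whether a reduction "can be detected by a McNemar Test for paired proportions". It states no side, no correction, and no choice between the exact and asymptotic forms. It treats the result as exploratory and expects low power relative to the best case used for sizing.

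The sentence in 10.1.2 that reports the two pilot rates also attaches the higher one to the wrong device: it reads "with the device C-Brace and a probability to fall more", although the symbol beside the number is the KAFO/SCO one.

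**The concern.** With a planned rate of zero on C-Brace, every discordant pair points the same way, and about 6 such pairs are expected among 45. A normal approximation to so small a count need not give the right power, so the 0.8 has to be checked by enumeration.

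The second issue is the gap between the sizing and analysis sections. One section names a specific version and then doubts it; the other names none. With so few discordant pairs, the versions differ by several patients in what they call significant. A result of 4 against 0 is significant with either uncorrected Z-test but not with an exact or corrected test. Section 10.1.2 says a significant result could be used to support the relevance of the primary finding, and section 10.4 allows conditional testing of selected secondary objectives at the interim. A test with those uses should have its rejection rule fixed in advance.

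**Working it through.** **1. Inputs.** From 10.1.2: p(KAFO/SCO) = 0.1333 (2 of 15), p(C-Brace) = 0, so p_diff = p_disc = 0.1333; one-sided alpha 0.05; power 0.8; dropout 20%. 56 × 0.8 = 44.8, or about 45 pairs.

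**2. The plan's figure reproduced.** n = ((z₀.₉₅√p_disc + z₀.₈₀√(p_disc − p_diff²)) / p_diff)². The two terms in the numerator are 1.645 × √0.1333 = 0.6005 and 0.8416 × √(0.1333 − 0.0178) = 0.2861. Then (0.8866 / 0.1333)² = 44.24, agreeing with 44.2386. 44.2386 / 0.8 = 55.3, rounded up to 56. The same approximation gives a power of 0.806 at 45 pairs.

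**3. Rejection limits when all discordant pairs favour C-Brace (r against 0).**

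- One-sided uncorrected Z: r/√r > 1.645. For r = 2 it is 1.414, for r = 3 it is 1.732. Limit 3.
- Two-sided uncorrected Z: r/√r > 1.960. For r = 3 it is 1.732, for r = 4 it is 2.000. Limit 4.
- One-sided exact: 0.5⁴ = 0.0625, 0.5⁵ = 0.031. Limit 5. Corrected Z: (4 − 1)/√4 = 1.5, (5 − 1)/√5 = 1.789. Also 5.
- Two-sided exact: 2 × 0.5⁵ = 0.0625, 2 × 0.5⁶ = 0.031. Limit 6. Corrected Z: 1.789 at r = 5, (6 − 1)/√6 = 2.041 at r = 6. Also 6.

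**4. Power.** With p(C-Brace) = 0, the discordant count is Binomial(45, 0.1333), mean 45 × 0.1333 = 6.0. The probabilities of 0 to 5 are 0.0016, 0.0111, 0.0375, 0.0826, 0.1334 and 0.1682. Power is one minus the sum below the limit.

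| Version | Limit | Power, 45 pairs | Power, 44 pairs | Pairs for power ≥ 0.8 |
|---|---|---|---|---|
| One-sided Z, uncorrected | 3 v 0 | 0.950 | 0.944 | 31 |
| Two-sided Z, uncorrected | 4 v 0 | 0.867 | 0.855 | 41 |
| One-sided exact or corrected | 5 v 0 | 0.734 | 0.715 | 50 |
| Two-sided exact or corrected | 6 v 0 | 0.566 | 0.543 | 58 |

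**5. Size of the named test.** Enumerated at 45 pairs under equal rates, the one-sided uncorrected Z-test rejects with probability about 0.046 to 0.052 for discordant proportions from 0.067 to 0.267 (0.049 at 0.1333). The one-sided exact test has size 0.004 to 0.027 over the same range.

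**6. Sensitivity (assumed C-Brace rates, not from the documents).** p(KAFO/SCO) is held at 0.1333, and p_disc is the sum of the two rates, as in the plan, so no patient falls more than once on both devices. Both tests are one-sided at 45 pairs.

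| Assumed p(C-Brace) | p_diff | p_disc | Power, Z | Power, exact or corrected | Pairs by the plan's formula |
|---|---|---|---|---|---|
| 0 | 0.1333 | 0.1333 | 0.95 | 0.73 | 45 |
| 0.01 | 0.1233 | 0.1433 | 0.79 | 0.59 | 57 |
| 0.02 | 0.1133 | 0.1533 | 0.66 | 0.47 | 72 |
| 0.033 | 0.1003 | 0.1663 | 0.52 | 0.35 | 101 |

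Zero events in 15 pairs leaves much room: the one-sided 95% upper limit is 1 − 0.05^(1/15) = 0.18.

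**The case against.** The best defence is that the plan does name a version in 10.1.2, that its arithmetic is right for the formula it prints, and that under its own assumptions this version has more power than claimed. The plan also warns that a correction may be preferable, that rates above zero would be costly, and that the test will probably be underpowered. Every secondary p-value is exploratory. All of this stands and limits the point to a restated figure and an unfixed test. It does not remove the point: the warnings carry no numbers, and the version named for sizing is not repeated where the analysis is specified.

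Four stronger readings are tempting, and the documents do not support them.

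- **That the sample size arithmetic is wrong.** It reproduces exactly; the weakness is the approximation.
- **That the trial is too small.** With the named test and a C-Brace rate of zero it is not. Power falls below 0.8 only with an exact or corrected test, or with a C-Brace rate above zero, which the plan itself concedes would be costly.
- **That the uncorrected test is too liberal because it rejects on 3 against 0, where the exact one-sided p is 0.125.** Its size at 45 pairs stays close to 0.05 over the range examined.
- **That the swapped device names undermine the calculation, or show that the pilot favoured the comparator.** The symbols, the difference and the discordant proportion all run the other way, and no computed number uses the swapped wording.

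**Conclusion.** The point holds in a limited form. The stated power of 0.8 is not the real power of any of the four versions examined. At 45 pairs the real figures run from 0.95 for the test named in the sizing section to 0.57 for a two-sided exact or corrected test. The analysis section leaves that choice open, which moves the rejection limit from 3 against 0 to 6 against 0.

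These figures assume 45 evaluable pairs, a KAFO/SCO rate of 0.1333 and a C-Brace rate of exactly zero. The range is 0.54 to 0.94 at 44 pairs, and power drops quickly once the C-Brace rate is above zero. The consequence is confined to an exploratory secondary test. It deserves correction because the trial size is stated to rest on this figure, but nothing in the confirmatory Berg Balance Scale analysis depends on it.

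**What to change.** Keep 56 patients, and make these changes before any falls data are analysed, including at the interim.

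1. **Section 10.3.1 (Secondary outcome analysis):** name one version, side and level. The least change is to carry over the one-sided uncorrected Z-test at 0.05 from 10.1.2. The one-sided exact or continuity-corrected test is the alternative.
2. **Section 10.1.2:** replace the stated power of 0.8 with the enumerated power of the chosen test at 45 pairs: 0.95 for the Z-test, or 0.73 for the exact or corrected test, if the C-Brace rate is zero.
3. **Section 10.1.2:** add a sensitivity line, labelled as an assumption. Power would be 0.66 (Z) or 0.47 (exact or corrected) at a C-Brace rate of 0.02, and 0.52 or 0.35 at 0.033. The plan's formula would need 57, 72 and 101 pairs at 0.01, 0.02 and 0.033.
4. **Editorial:** check the device names in the sentence giving the two pilot rates against the pilot data, and correct them.

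The cost is wording only, with no extra patients. The downside is that the stated power looks less favourable once the C-Brace rate is above zero.

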10.2 Management of missing, unused or spurious data

If data are missing, illegible or incoherent, requests for further information will be sent to the investigator in question. Although every effort will be made to ensure that each patient's data is complete, some patients may not have data on one or more measures.

For the intention-to treat analysis the missing data will be imputed. The imputation method will depend on whether the missing data are at baseline or follow-up visit as well as the reason for the missing data as further described below.

Missing baseline data for patients will be imputed. For missing data in any of the measurements which are taken again at the second baseline, these values might be used in place of the first baseline measurement. Evaluation whether other missing baseline data might not be missing at random, will be done by exploring patterns of missing data within different measurements and patients for which data was collected.

Strong evidence for missing data patterns within measurements of secondary interest may lead to the exclusion of such measurements for any supportive analysis and will be documented in the study

ottobock.	CLINICAL INVESTIGATION PLAN	Document number:	PD-PS00120016A-001
		Version number:	7
Project name	Clinical trial comparing C-Brace to KAFO/SCO	Project no.	PS00120016A

report accordingly. In case such a pattern is observed within the measurement of primary interest may lead to the study being declared invalid in regard to the analysis planned for it.

Appropriate data management as defined in the protocol should reduce the chance of this being the case. Strong evidence for missing data patterns within patients of specific characteristics will be evaluated and might be indicative of a serious limitation to the study and could potentially lead to the study being declared invalid. Previous studies on the topic have not shown this to be very likely in the patients that fulfill the inclusion criteria of the study. Where data is assumed to be missing at random multiple imputation and a sensitivity analyses will be used.

In order to perform a sensitivity analysis, patients who terminated treatment early, will be imputed using multiple imputation methods in order to substitute missing values. Here, multiple copies of the original dataset will be generated by replacing missing values using e.g. a multivariate normal distribution. Each of these complete sets will be analyzed as complete sets and the corresponding parameter and standard error estimates will be combined with taking the uncertainty of the imputation process into account.

For the patients missing follow-up data, proportions of missingness, type of missing measurements, patient characteristics and baseline value levels will be explored in order to detect patterns of missing data. If data is assumed to be missing at random the following imputation strategy will be used.

A linear mixed effects model with the outcome measure as dependent variable will be fitted to the data. This model will use the treatment group and period as fixed factor and the first baseline measure as covariate. Random patient effects will be introduced for the intercepts and thus taking the correlation within patients into account. The analysis implicitly uses a weighted average to estimate the outcome measures, with estimations coming from the complete observations and from the observations with missing values.

Missing data for study patients at follow-up on C-Brace, KAFO/SCO or both because they 1) died, 2) are lost to follow-up (LTFU), 3) withdrew from the study or were withdrawn from the study by the investigator, 4) miss the follow-up visit or 5) do not complete the outcome measure at follow-up, will be imputed by using a mixed model with a random intercept for patient and treatment group as predictor variables.

The details of the imputations methods applied will be documented in the study report.

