All data management activities will be conducted by the sponsor or a sponsor's designee following their SOPs. The database will be built by the sponsor or a sponsor's designee.

Details on data handling will be described in the Data Management Plan. The sponsor or the sponsor's designee will handle the data cleaning process, including logical check, and query processes. Computerized validation check programs on completeness, correctness, plausibility (such as range checks, crosschecks) will verify the data according to the Data Validation Plan. All identified discrepancies will be addressed to the investigator.

The database will be hard locked after all the changes following the data review meeting have been done and the database is considered complete and accurate. All changes will be tracked (audit trail).

15 Documentation and administration

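### Section 10.2 permits outcomes to be excluded or the study declared invalid on an undefined missing-data pattern, and plans no sensitivity analysis for data not missing at random

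*Combined protocol and SAP*

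**What the plan says.** Section 10.2 first covers missing baseline data, which are to be imputed, with the second baseline available as a substitute where the measure is repeated there. Patterns are then explored to judge whether other missing baseline data might not be missing at random. Three consequences follow:

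- **Secondary measurements.** Strong evidence of a pattern "may lead to the exclusion of such measurements for any supportive analysis", and this is to be documented in the study report.
- **Primary measurement.** Such a pattern "may lead to the study being declared invalid in regard to the analysis planned for it".
- **Patient characteristics.** A pattern among patients of particular characteristics is to be evaluated as a possible serious limitation and "could potentially lead to the study being declared invalid".

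On methods, the same section states: "Where data is assumed to be missing at random multiple imputation and a sensitivity analyses will be used". For missing follow-up data it says: "If data is assumed to be missing at random the following imputation strategy will be used". The strategy is a linear mixed model with treatment and period as fixed factors, first baseline as covariate and a random patient intercept. A later paragraph imputes follow-up values missing through death, loss to follow-up, withdrawal, a missed visit or an uncompleted measure, again by a random-intercept mixed model.

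Section 10.3.2 makes the ITT mixed model for BBS the confirmatory analysis. On data handling, section 14 says: "All data management activities will be conducted by the sponsor or a sponsor's designee following their SOPs". The trial is open-label (section 7).

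**The concern.** Rules that decide which results count should be fixed before the data are seen. Here the trigger is strong evidence of a pattern, found by exploration. It has no threshold or test, no named decision-maker, no timing relative to unblinded results and no blinding. All three consequences are optional.

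The rules also sit badly with the rest of the plan. Section 10.2 says missing ITT data will be imputed and section 10.3.2 makes the ITT model confirmatory, yet a pattern could set that analysis aside. The third rule treats missingness related to patient characteristics as possible grounds for invalidity. Missingness explained by recorded characteristics is compatible with MAR and can be handled by including those characteristics in the imputation model.

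Such patterns are foreseeable in this trial. Lockdowns interrupted visits (section 7.3.12), and the COVID-19 risk assessment considers age, lung and kidney disease, cancer and obesity before a site visit is arranged (section 17.3). Home use requires passing the Level 1 benchmark (section 7.3.4.3), so a patient who cannot manage a device may have no follow-up BBS on it, which is plausibly informative. In that case the plan offers no analysis showing how far the conclusion depends on MAR.

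**Working it through.** **Rules against methods.** Section 10.2 gives two tools, multiple imputation and the random-intercept mixed model. Both are tied to MAR by its text or rest on it by construction. No delta-adjusted, reference-based or other analysis under missing not at random (MNAR) appears anywhere in the documents.

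**Sample size used in the illustration.** Section 10.1.2 uses a one-sided McNemar test with discordant proportion and difference both 0.1333:

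n = ((1.645·√0.1333 + 0.8416·√(0.1333 − 0.1333²)) / 0.1333)² = 44.2386

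44.2386 / 0.8 = 55.3, rounded up to 56. The plan's figure is reproduced.

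**Inputs to the tipping point.** The planned mean difference 6.6429 and SD 4.9085 are from section 10.1.1. The 20% dropout and N = 56 are from section 10.1.2, and the 3-point line is from rule 2 of section 10.4. Assumptions of mine: one-sided 0.05 applied to a simple paired mean, 20% of the 56 missing, the same SD within missing patients as within completers, and 4 points as a less favourable completer effect.

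Let μ be the completers' mean device difference and d that of the missing patients.

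- Overall mean: M = 0.8μ + 0.2d
- Overall variance: V = 4.9085² + 0.8·0.2·(μ − d)², because two groups with different means widen the spread
- Significance is lost when M = 1.673·√(V/56), where 1.673 is the one-sided 5% t value on 55 degrees of freedom

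*Planned effect, μ = 6.6429.* At d = −15.3 the gap is 21.96.
- M = 5.314 − 3.064 = 2.25
- √V = √(24.09 + 77.19) = 10.06
- Critical mean = 1.673·10.06/√56 = 2.25, so d = −15.3 is the tipping value.

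*Effect of 4.* At d = −8.25 the gap is 12.25.
- M = 3.2 − 1.65 = 1.55
- √V = √(24.09 + 24.00) = 6.94
- Critical mean = 1.673·6.94/√56 = 1.55, so d = −8.2 is the tipping value.

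*Mean pulled down to 3 points* (no SD involved): d = (3 − 0.8μ)/0.2.
- Effect 6.6429: (3 − 5.314)/0.2 = −11.6
- Effect 4: (3 − 3.2)/0.2 = −1.0

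| Completer effect | Loses significance at d | Mean falls to 3 at d |
|---|---|---|
| 6.64 | −15.3 | −11.6 |
| 4 | −8.2 | −1.0 |

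**Range over the number missing.** At the planned effect, the missing patients' mean that brings the estimate to 3 is 6.6429 − 3.6429/(m/56). This gives −27.4 for m = 6, −11.9 for m = 11 and −5.4 for m = 17.

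**A fragile case.** Assume completers with mean 3 and SD 10, and 11 missing. Even with the standard error held at the completers' value, the critical mean is 1.680·10/√45 = 2.50. The tipping shift is (3 − 2.50)/(11/56) = 2.5 points.

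**The case against.** **Scope.** The secondary and primary clauses follow directly on the text about missing baseline data, while missing follow-up data are treated later in the section without any such clause. Read as baseline-only, the primary clause has little reach. BBS is measured at screening because it is an eligibility criterion, the screening value may serve as first baseline if taken within 24 hours (section 7.3.2.2), and the second baseline can substitute. This reading is fair, and a delta adjustment of follow-up values would not address a missing baseline. But both clauses are worded generally and the patient-characteristics clause is broader. Confined to baseline, invalidity would be harder to justify still, since a missing covariate has little influence on a within-patient contrast.

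**Motive and decision-maker.** A reader might infer that the sponsor decides and could void an unfavourable primary result. The documents do not say so. Section 10.2 names nobody, section 14 gives data management to the sponsor or a designee, and the trigger is a missingness pattern rather than a result. The clauses can be read as cautious statements of limitation. What stands is that nothing in the text restricts the discretion.

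**Dropped outcomes.** The exclusion concerns supportive analysis, must be documented, and affects outcomes whose inference is exploratory under the secondary outcome analysis section. It is narrower than removing an outcome from the report.

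**MAR or nothing.** A reader might infer that the only alternative to assuming MAR is to discard the result. That goes too far. Section 10.2 says missing ITT data will be imputed, its last method paragraph imputes for five listed reasons without requiring a MAR judgement, and section 10.3.2 commits to the ITT model. A default result exists; what is missing is any test of its dependence on MAR.

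**Choice of method.** A tipping-point analysis is one of several MNAR options and cannot show whether data are MNAR. It shows only whether the conclusion survives departures from MAR.

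**Conclusion.** The point holds. Section 10.2 contains three open-ended options to exclude or invalidate, with no threshold or decision-maker. All its stated methods rest on MAR, and no MNAR sensitivity analysis is planned. Missingness explained by recorded characteristics is not in itself a reason for invalidity.

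The figures show that the replacement is informative. They do not forecast that the trial will be robust. A calculation holding the SD at 4.91 would put the significance tipping values at −21.1 and −10.5, which overstates robustness because a shifted subgroup also widens the spread. Nor does it follow that strong non-random missingness is harmless: at an effect of 4, missing patients averaging only −1 bring the mean down to the 3-point line.

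The illustration depends on the assumed 20% missing, the equal SD within missing patients, and a paired mean standing in for the mixed model. The textual finding depends on none of these.

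**What to change.** In section 10.2:

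1. Delete all three options: exclusion of secondary measurements, invalidity from a pattern in the primary measurement, and invalidity from a pattern by patient characteristics.
2. State that the ITT mixed model for BBS and all pre-specified secondary outcomes are reported whatever the missing-data pattern, with limitations described.
3. Include in the imputation model the recorded characteristics found to predict missingness.
4. Pre-specify a delta-adjusted tipping-point analysis for missing follow-up BBS. Impute under MAR, subtract delta from the imputed C-Brace values starting at 0, increase it until the conclusion changes, and report that delta. State the range in advance, and report both the loss of significance and the crossing of the 3-point line.

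This uses the multiple imputation already planned and leaves sample size, visits and trial conduct unchanged. The cost is SAP wording and one added sensitivity analysis.
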